Can Mental Health Chatbots Help Chronic Disease Populations?

[Evaluating the Usefulness of an Artificial Intelligence (A.I.) Mental Health Chatbot in a Healthcare Setting]

Protocol and Statistical Analysis Plan

NCT04620668

October 15, 2020

Updated February 13, 2024 for title page, formatting

People dealing with chronic health conditions are susceptible to mental health issues such as depression and anxiety (Clarke & Currie, 2009). Providing conventional mental health services to all of these individuals is not practical given the limited resources of the healthcare system. Artificial intelligence (A.I.) mental health chatbots may be an accessible and costeffective means by which people can receive some degree of mental health support while they cope with their conditions. These automated programs act as a source of virtual support, talking with individuals and providing them with therapeutic exercises to improve their mental wellbeing. Several chatbots have been designed to deliver interventions based on popular psychological therapies (e.g., Wysa, Woebot, and Tess). Research has shown that these programs can reduce symptoms of depression, anxiety, and stress in nonclinical populations (Fitzpatrick et al., 2017; Fulmer et al., 2018; Inkster et al., 2018; Ly et al., 2017). However, the effectiveness of these programs has not been tested in chronic disease populations.

The purpose of the current research is to gain a better understanding of the usefulness of mental health chatbots for chronic disease populations. This research will be guided by two fundamental objectives: (1) to determine whether a mental health chatbot can reduce or prevent negative mental health symptoms in individuals who are dealing with a chronic health condition, and (2) to learn more about how individuals with a chronic health condition view these programs, particularly in terms of their potential benefits or drawbacks when used in healthcare settings. This research will focus on two specific chronic disease populations that are prone to elevated levels of mental health symptoms: people with arthritis and diabetes.

Method

Design

The study objectives will be pursued using a mixed-method research design (Creswell & Plano Clark, 2011), which will involve collecting and analyzing quantitative data on individuals' mental health symptomology and qualitative data on their experiences with the mental health chatbot.

Sample

Participants will be individuals between the ages of 19 and 65 who have a diagnosis of diabetes (type 1 or type 2 diabetes) or arthritis (osteoarthritis, rheumatoid arthritis, or another type of arthritis). Although people of any age might be susceptible to mental health issues when dealing with these conditions, individuals in the young adult and middle adult age groups may be at particularly high risk because they have to navigate certain life obligations while coping with their conditions (e.g., caring for a young family, working a job) that many older and younger individuals do not. They are also more likely to use and be familiar with chat-based programs than young children or older adults, meaning that they will almost certainly have the modest technical knowledge required to complete the study.

A power analysis conducted using G*Power (Heinrich-Heine-Universität, Düsseldorf) indicated that a total of 40 participants would be required for the quantitative portion of the study, assuming a moderate effect size, .80 power, an alpha level of .05, and a moderate correlation between repeated measures (.50). However, a larger number of participants (N = 60) will be sought to strengthen the analysis. Individuals will be excluded from participation if they are receiving ongoing treatment from a mental health professional, if they already use a mental health chatbot, or if they started or experienced a dosage change in a psychopharmacological drug within the previous month. Participants will also need to have a phone with an active Internet connection. Participants will be offered a \$20 gift card (Canadian funds) to an online retailer of their choice for completing the study. Participants who drop out of the study prior to

completion will be eligible for a \$5 gift card. An additional \$10 gift card will be offered to participants in the treatment group who complete an optional interview following the main study. **Setting**

The study researchers will be based at the Centre for Research in Integrated Care (CRIC) at the University of New Brunswick in Saint John. The centre will provide access to workspace and necessary equipment and software. All participant communication will occur remotely through phone calls, videoconferencing, and/or email. The developer of the chatbot, Touchkin eServices, will provide technical support and assistance to the research team as necessary from their location Bengaluru (Bangalore), India.

Procedure

Participants will be recruited through social media channels (including online groups), newspaper advertisements, and emails and newsletters from relevant organizations (e.g., the Arthritis Society, Diabetes Canada). After volunteering to participate, participants will set up a phone or video conferencing call with the primary investigator to orient them into the study. Participants will be randomly assigned to either a treatment group or control group. Those assigned to the treatment group will download the mental health chatbot Wysa (Touchkin eServices, Bangalore) on their smartphones. They will be encouraged to interact with the chatbot at least two times per week over a period of four weeks. Participants assigned to the control group will receive no chatbot (i.e., they will be in a no-treatment control group).

Regardless of their group assignment, participants will complete online materials via Qualtrics at the outset of the study, two weeks into the study, and four weeks into the study (i.e., the final assessment point). At the outset of the study, participants will fill out an informed consent form, a demographic questionnaire, and four psychological assessments tools: measures of depression (Patient Health Questionnaire; Kroenke et al., 2001), anxiety (Generalized Anxiety Disorder Scale; Spitzer et al., 2006), stress (Perceived Stress Scale; Cohen & Williamson, 1988), and life satisfaction (Satisfaction with Life Scale; Diener, et al., 1985). Two weeks into the study, participants will complete the four psychological assessment tools a second time. Four weeks into the study, participants will complete the four assessment tools a final time, and those in the treatment group will be presented with a post-study questionnaire that contains qualitative questions regarding their experiences with the chatbot. Participants in both groups will be presented with a debriefing form providing more information about the study. Those in the control group will be given the opportunity to download and use the chatbot.

To facilitate participant compliance, email reminders about outstanding surveys will be sent throughout the week as necessary. In addition, participants in the treatment group will be sent a general reminder about the intervention once per week.

After the data from the four-week study are analyzed, a subset of participants from the treatment group may be asked to complete optional phone or video interviews to gain more insight into their experiences with and opinions on the chatbot. Approximately 15 to 20 participants will be sought for the interviews. The questions for these interviews will be developed based on the collective results from the quantitative and qualitative analysis described above.

Data Analysis

Quantitative data will be entered into SPSS version 26 (IBM Corp., Armonk, NY, USA) for statistical analysis. Comparisons between the treatment and control groups will be performed using four mixed analysis of variance (ANOVA) statistical tests, with experimental group and health condition as the between-subjects factors, time point as the within-subjects factor, and

mental health outcomes (i.e., scores on the Patient Health Questionnaire, Generalized Anxiety Disorder Scale, Perceived Stress Scale, Satisfaction with Life Scale) as the dependent variables. Significant interactions will be followed up with repeated measures ANOVAs (one within each experimental group) and dependent t-tests with Bonferroni adjustments, as needed.

Qualitative data will be analyzed using Braun and Clarke's (2006) six phases of thematic analysis: (1) familiarize oneself with the data; (2) generate initial codes; (3) search for themes; (4) review themes; (5) define and name themes; and (6) provide the report. This analysis will be performed on the qualitative data from the post-study questionnaire as well as the phone or video interviews. Qualitative data management will be performed with the assistance of NVivo version 12 (QSR International, Burlington, MA, USA).

Implications

There would be several positive implications if results show that a mental health chatbot can help people with chronic health conditions manage their mental health symptoms. Although these types of programs are not a replacement for more conventional mental health providers, they would be an accessible and cost-effective means by which people could gain some degree of mental health support while they are coping with their chronic health conditions. People who do not have access to a mental health provider (e.g., those who live in rural communities or who have reduced mobility due to their health conditions) and those who lack the means to pay for a mental health provider on their own (e.g., low income individuals) would be able to receive some mental health support within the comfort of their own homes for little or no cost. These programs would also be an invaluable tool for helping people with chronic health conditions cope when experiencing socially mandated restrictions on their mobility (e.g., self-isolation during a pandemic).

Despite this positive potential, participants in the current study will almost certainly identify limitations with these programs as well. These limitations could include technical limitations with the program itself (e.g., conversations may lack a certain degree of naturalness), as well as limitations in terms of the practical utility of these programs (e.g., there is no possibility of interprofessional collaboration in situations where this would be beneficial). This type of feedback could be useful for the future refinement of these programs. It could also help to inform policy decisions on how these programs should be used in a healthcare context, or even whether they should be used at all.

References

Braun, V., & Clarke, V. (2006). Using thematic analysis in psychology. *Qualitative Research in Psychology*, *3*(2), 77-101. doi: 10.1191/1478088706qp063oa

Clarke, D.M. and Currie, K.C. (2009). Depression, anxiety and their relationship with chronic diseases: A review of the epidemiology, risk and treatment evidence. *Medical Journal of Australia, 190*(S7), S54-S60. doi:10.5694/j.1326-5377.2009.tb02471.x

Cohen, S., & Williamson, G.M. (1988). Perceived stress in a probability sample of the United States. In S. Spacapan & S. Oskamp (Eds.), *The social psychology of health: Claremont Symposium on Applied Social Psychology* (pp. 31-67). Sage.

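### The arms are compared only through mixed ANOVAs with baseline as an outcome and within-arm follow-ups, so no baseline-adjusted between-arm estimate at week 4 is planned

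*Combined protocol and SAP*

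**What the plan says.** The first objective, in the introduction, is "to determine whether a mental health chatbot can reduce or prevent negative mental health symptoms in individuals" with a chronic condition. Under Procedure, all four scales are completed at the outset, at two weeks and at "four weeks into the study (i.e., the final assessment point").

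Under Data Analysis, the treatment and control groups are compared with four mixed ANOVAs, one per scale, "with experimental group and health condition as the between-subjects factors, time point as the within-subjects factor". The next step is: "Significant interactions will be followed up with repeated measures ANOVAs (one within each experimental group) and dependent t-tests with Bonferroni adjustments", as needed. No other between-arm analysis appears. Baseline is never named as a covariate.

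The Sample section states that "a total of 40 participants would be required for the quantitative portion of the study, assuming a moderate effect size, .80 power", with "an alpha level of .05, and a moderate correlation between repeated measures (.50"), and that "a larger number of participants (N = 60) will be sought to strengthen the analysis". It gives no number for the moderate effect and does not name the G*Power test or the contrast. It provides for people who drop out but gives no rate.

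**The concern.** Objective 1 is a question about the difference between arms. The only planned test that bears on it with reasonable power is the arm-by-time term, which has 2 df and asks whether the pattern over three time points differs between arms. A significant result does not say where the arms differ. The follow-ups cannot say so either: a significant change in the chatbot arm and a non-significant one in the control arm can occur without any difference between the arms. The report could thus rest on two within-arm results, with no estimate of the chatbot's effect at week 4 and no interval to help read a null result.

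A second cost is efficiency. The baseline score is already collected, and using it as a covariate rather than as an outcome level would usually sharpen the comparison.

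**Working it through.** **Inputs.** From the Sample section: power .80, alpha .05, correlation ρ = .50, N = 40 and 60. From Procedure: three time points. From Data Analysis: 2 arms × 2 conditions = 4 cells. Assumed, because the plan does not state them: equal arms and cells, no dropout, equal SDs (set to 1), and compound symmetry.

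**The plan's own figure.** Reading moderate as f = .25 (an assumption), with four cells and three time points, λ = f²·N·3/(1−ρ) = .0625 × 40 × 3/.5 = 15, with (4−1)(3−1) = 6 and (40−4) × 2 = 72 df. Power is .805, so 40 reproduces, for the four-cell-by-time interaction. The same f with two groups (the 2-df arm-by-time term) gives 28.

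**Planned 2-df arm-by-time term, N = 60.** λ = (N/4)·Σ(δₜ − mean δ)²/(1−ρ), with 2 and 2(60−4) = 112 df; .80 power needs λ = 9.90.
- Step (0, d, d) or late (0, 0, d): λ = d²N/[6(1−ρ)], so d = √(9.90 × 3/60) = 0.70.
- Linear (0, d/2, d): λ = d²N/[8(1−ρ)], so d = √(9.90 × 4/60) = 0.81.

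**Week-4 score on arm, condition and baseline, N = 60.** λ = d²N/[4(1−ρ²)], with 1 and 56 df; .80 power needs λ = 8.13, so d = √(8.13 × 3/60) = 0.64 for any of these shapes. A small allowance for chance baseline imbalance leaves it at 0.64 (0.643).

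**Where the gain comes from.** At ρ = .50 the step or late λ and the adjusted λ are both d²N/3. For those shapes the whole gain is one numerator df instead of two. Only for linear divergence does the planned test also have a smaller λ (d²N/4).

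| Power at a true week-4 difference of 0.64 SD, N = 60 | λ | Power |
|---|---|---|
| Planned test, step or late | 0.4096 × 60/3 = 8.19 | .72 |
| Planned test, linear | 0.4096 × 60/4 = 6.14 | .58 |
| Baseline-adjusted week 4 | 8.19 | .80 |

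Simulation (20,000 runs per setting) gave .717, .582 and .796–.798.

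**Does the arm main effect fill the gap?** It averages in baseline, where randomised arms should not differ. At 0.64 SD and N = 60 its power is .51 (step), .32 (linear) and .17 (late).

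**Does a significant interaction imply a week-4 difference?** No. With arms 0.70 SD apart at week 2 and equal at week 4, λ = 0.49 × 60/3 = 9.8 and the interaction test has power .80. The adjusted week-4 test rejects 5% of the time, as it should.

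**Sensitivity, detectable SD at .80 power.**

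| Setting | Planned (step or late to linear) | Adjusted week 4 |
|---|---|---|
| N = 60, ρ = .3 | 0.83–0.96 | 0.70 |
| N = 60, ρ = .5 | 0.70–0.81 | 0.64 |
| N = 60, ρ = .7 | 0.55–0.63 | 0.53 |
| N = 60, ρ = .82 | 0.42–0.49 | 0.42 |
| N = 48 (illustrative 20% loss: 60 × .8), ρ = .5 | 0.79–0.91 | 0.72 |
| N = 60, baseline-to-week-4 correlation .35 | not computed | √(8.13 × 4 × (1 − .1225)/60) = 0.69 |

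The last row lets correlation decay with time (.575 between adjacent visits, .35 from baseline to week 4, averaging .50). At 0.64 SD the adjusted power is then about .73, against about .69 (step or late) or .55 (linear) for the planned test.

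**The case against.** The strongest reply is that a mixed ANOVA with an arm-by-time term is a valid, conventional comparison of randomised arms, with nominal type I error when simulated under compound symmetry (.046–.049). Objective 1 names no time point, and calling week 4 the final assessment describes the schedule; it does not make week 4 primary. Sensitivity to a week-2 difference is therefore not itself a defect. The 0.64 SD is in no part of the plan; it is simply what the adjusted test can detect, so scoring the planned test against it favours the alternative. At 0.5 SD the adjusted test at N = 60 would itself have only 59% power. All of this stands, and it limits the efficiency argument to a modest one.

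A reader might go further and infer that 40 was miscalculated or that the trial is underpowered. The documents do not support either. The 40 reproduces at f = .25. In that convention f = .25 on the arm-by-time term corresponds to .25 × √18 = 1.06 SD (step or late) to .25 × √24 = 1.22 SD (linear), for which the 2-df test has power of about .93 at 40 and .99 at 60. With no numeric effect in the plan, no shortfall can be shown.

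The reply does not reach the other half of the point. Whatever the correlation or effect size, the follow-ups are within-arm only, and no between-arm estimate or interval at week 4 is specified.

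**Conclusion.** The point holds as one of analysis and efficiency, not of arithmetic. As written, the plan cannot deliver a between-arm estimate at the final assessment, and its within-arm follow-ups cannot establish that the arms differ there. This part rests on the text alone.

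The efficiency part is conditional on equal arms, complete data, compound symmetry and correlation .50: 0.70–0.81 SD against 0.64 SD at 60. It is worthwhile for linear divergence, modest for a step or late effect, small at correlation .7, and gone for step or late effects near .82. The 0.64 SD is a best case. The change is worth making because it is cheap and answers objective 1 directly, not because the sample size is wrong.

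**What to change.** Add to Data Analysis, before the data are analysed:

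> For each scale, objective 1 will be answered by the difference between arms at week 4 from a linear model with arm, health condition and baseline score, reported with its 95% confidence interval. The mixed ANOVA will be reported alongside. A difference between arms will not be inferred from the within-arm follow-up tests.

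A repeated-measures model of weeks 2 and 4 with baseline as covariate, from which the week-4 difference is taken, would serve equally.

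If a detectable difference is stated, give it as a range with its assumptions: at .80 power and alpha .05, about 0.64 SD with 60 analysed and 0.72 SD with 48 at correlation .50, and about 0.69 SD with 60 if the baseline-to-week-4 correlation is .35.

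The cost is one extra model per scale in the same software, with no added participants, visits or measures. A benefit at week 2 only would not count in the week-4 comparison, though the retained mixed ANOVA would still show it.

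### Does the power statement fail to support 40 participants because it does not name the ANOVA effect it was computed for?

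*Combined protocol and SAP*

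**What the plan says.** The Sample section of the combined protocol and SAP gives the only sample-size justification. It puts the requirement as "a total of 40 participants would be required for the quantitative portion of the study". The inputs listed for this figure are "assuming a moderate effect size, .80 power, an alpha level of .05, and a moderate correlation between repeated measures (.50"). The recruitment target is then raised: "a larger number of participants (N = 60) will be sought to strengthen the analysis". The effect size is given in words only. The G*Power test, the number of groups, the number of measurements and the nonsphericity correction are not listed there.

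Other sections supply part of this. The Procedure section sets three assessments (outset, two weeks, four weeks) and two arms: "Participants will be randomly assigned to either a treatment group or control group". The Data Analysis section says "Comparisons between the treatment and control groups will be performed using four mixed analysis of variance (ANOVA) statistical tests". The model is set up "with experimental group and health condition as the between-subjects factors, time point as the within-subjects factor". That makes four between-subjects cells measured three times. It continues: "Significant interactions will be followed up with repeated measures ANOVAs (one within each experimental group"), with Bonferroni-adjusted dependent t-tests as needed. No sentence declares one effect to be the treatment test.

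**The concern.** A repeated-measures power calculation depends heavily on which effect is powered, because the correlation between visits helps a within-subjects contrast and hurts a between-subjects one. With the effect unnamed, the listed inputs do not by themselves fix a sample size.

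Each planned ANOVA has four effects that involve the randomised group: group, group-by-condition, group-by-time and the three-way interaction. With four outcomes, 4 × 4 = 16 results could in principle be presented as the treatment result. If the group main effect were meant, 60 participants would fall short of .80 power. A reader might also take a moderate effect to be half a standard deviation at week 4, which is not what f = .25 means for an interaction.

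**Working it through.** **Inputs.** Alpha .05, power .80 and correlation ρ = .50 (Sample section); m = 3 visits (Procedure); two arms by two conditions, four cells (Data Analysis). Assumed because not stated: f = .25 for moderate, equal cells, compound symmetry, ε = 1.

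**Formulas (noncentral F).**
- Within-subjects interactions: λ = f²·N·m/(1 − ρ), error df 2(N − 4).
- Between-subjects effects: λ = f²·N·m/(1 + (m − 1)ρ), error df N − 4.

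With the numbers in, λ = .0625 × 3/.5 × N = .375N for interactions with time, and λ = .0625 × 3/2 × N = .09375N for the group main effect.

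**The plan's figure.** Four groups and three measurements give (4 − 1)(3 − 1) = 6 numerator df. At N = 36, λ = 13.5 and power is .749. At N = 40, λ = 15 and power is .805. The smallest multiple of four reaching .80 is therefore 40, exactly as stated. That this was the entry used is an inference.

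**Other readings at f = .25.**

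| Effect | df | N for .80 | Power, N = 40 | Power, N = 60 |
|---|---|---|---|---|
| Group-by-time | 2 | 28 | .935 | .991 |
| Four cells by time, pooled | 6 | 40 | .805 | .954 |
| Group main effect | 1 | 86 | .470 | .645 |

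The 86 is the first even N; with four equal cells it is 88. The three-way interaction also has 2 df and needs 28.

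**Sensitivity.** With G*Power entries of two groups (group-by-time, group main effect) and four groups (pooled 6 df), N is 42, 134 and 64 at f = .20, and 20, 62 and 32 at f = .30. At ε = .75 and f = .25, group-by-time needs 34 and the pooled test 48, both within the target of 60.

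**Which effect the plan points to.** The only follow-up described is of interactions, by repeated-measures ANOVA inside each experimental group and then dependent t-tests. Those steps examine change over time arm by arm, which is how a group-by-time interaction is taken apart. No follow-up of a group main effect is described. That effect averages the pre-treatment visit with the two later ones, so it dilutes any treatment difference.

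**Whether the table compares like with like.** Let the between-arm difference be d·(0, a, 1) SD over the three visits. Then λ = N·d²·S/2, where S is the sum of squared deviations of (0, a, 1): S = .667 if the full effect is present by week 2, and .500 if it grows linearly. Setting this equal to .375N gives d² = .75/S, so d = 1.06 SD (full by week 2) or 1.22 SD (linear). For the group main effect, f = .25 is 0.5 SD at every visit, baseline included. The rows for 28 and 86 therefore describe different raw differences, and much of the gap comes from that.

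**What 60 can detect.** For group-by-time with 60 completers, 80% power needs λ of about 9.9. Solving 60·d²·S/2 = 9.9 gives d of about 0.70 SD (full by week 2) and 0.81 SD (linear). At ε = .75 these become 0.78 and 0.90 SD.

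**The case for a change.** The best case for a change is that a hint is not pre-specification. The follow-up sentence speaks of interactions in general, and each ANOVA has four, one of which (condition-by-time) does not involve treatment. The 6-df test that reproduces 40 pools group-by-time, condition-by-time and the three-way interaction, so the planned factorial ANOVA does not report it as an effect. In addition, power of .991 holds only on the f scale. For a week-4 difference of 0.5 SD, λ at N = 60 is 60 × .25 × .667/2 = 5.0 or 60 × .25 × .5/2 = 3.75, and power is about 49% (full by week 2) or 38% (linear).

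These facts stand. They show that the statement is brief and that moderate needs care in reading. They do not show a missed requirement. Entering four groups asks for more participants than group-by-time needs at the same f, so the entry errs on the safe side. The documents never promise power for 0.5 SD at week 4. Writing down the inputs and the effect name would leave the target of 60 and the four ANOVAs as they are.

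**Conclusion.** The concern is correct about what is left unsaid, but no change to the plan follows. The 40 is not an error: it matches a four-group, three-measurement within-between interaction at power .805. For group-by-time, the effect that the follow-up analyses imply, 40 gives .935 and the target of 60 gives .991. The unfavourable figures, 86 participants and 64.5% power at 60, belong to a reading that the plan points away from and to a different raw difference.

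This is a reporting gap that an analyst would fill sensibly by reading group-by-time as the treatment test. When results are written up, the detectable week-4 difference of about 0.70 to 0.81 SD tells the reader more than the word moderate.

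The conclusion rests on f = .25, sphericity, compound symmetry, even cells and, for the detectable difference, 60 completers. At ε = .75, 60 still exceeds what group-by-time needs at f = .25 (34), and at f = .20 with ε = 1 it does so as well (42).

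### The .80 power stated for a moderate effect at 40 participants does not hold for a moderate between-arm difference: the arm-by-time test detects 0.87 to 1.00 SD at 40 and 0.70 to 0.81 SD at 60

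*Combined protocol and SAP*

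**What the plan says.** The Sample section reports a G*Power result of 40 as the overall number needed for the quantitative part. The inputs it lists are: "assuming a moderate effect size, .80 power, an alpha level of .05, and a moderate correlation between repeated measures (.50"). It adds that "a larger number of participants (N = 60) will be sought to strengthen the analysis". It does not say which test was powered, which effect-size option was chosen, what numerical value stands behind the word moderate, or what difference in SD or scale points that value represents.

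The Data Analysis section states: "Comparisons between the treatment and control groups will be performed using four mixed analysis of variance (ANOVA) statistical tests". Arm and health condition are the between-subjects factors and time is the within-subjects factor. The Procedure section gives three assessments: outset, two weeks and four weeks. The analysis is therefore a 2 x 2 x 3 mixed ANOVA for each outcome. The term that carries the treatment question is arm by time, with 2 numerator df.

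**The concern.** A reader will take the Sample section to mean that 40 participants give .80 power for a medium-sized benefit of the chatbot over no treatment, and that 60 is a margin on top. In a repeated-measures interaction, however, the same nominal f stands for very different arm differences depending on how the program scales it. If the scale behind the 40 turns a nominally medium f into an arm difference above 1 SD, the stated power is not the power for a moderate treatment difference.

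At stake is how the result is read. The study's first objective is to determine whether a chatbot reduces or prevents symptoms, and readers will judge the result against the sensitivity that the plan claims.

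**Working it through.** **Inputs from the document.** Alpha .05, target power .80, correlation r = .50, stated N = 40 and sought N = 60 (Sample); m = 3 assessments (Procedure); k = 4 between-subjects cells, 2 arms x 2 conditions (Data Analysis).

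**Assumptions not in the document.** Moderate means f = .25, the conventional medium value. The test was G*Power's within-between interaction with its default effect-size option. Allocation is 1:1 with equal cells, sphericity holds, and there is no dropout. Baselines are equal and the effect is the same in both conditions. A moderate arm difference is 0.5 SD of a single measurement.

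**Step 1: reproduce the 40.** On the default scale, lambda = f² x N x m/(1 - r) = f² x N x 6, with df1 = (k - 1)(m - 1) = 6 and df2 = (N - k)(m - 1).
- N = 36: lambda = .0625 x 36 x 6 = 13.5, df2 = 64, power .749.
- N = 40: lambda = .0625 x 40 x 6 = 15, df2 = 72, power .805.

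With four equal cells, 40 is the smallest N reaching .80. Other settings at alpha .05 and f = .25 with sphericity give other totals: 28 (2 groups, 3 times), 34 (2 groups, 2 times), 48 (4 groups, 2 times), 86 or 124 (between-subjects main effect), 82 or 120 (SPSS effect-size option), 80 or 116 (Cohen option). A few settings with a smaller alpha also reach 40, but the plan states .05, and they use the same default scale.

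**Step 2: convert f = .25 to an arm difference.** Let g be the arm difference at each time point. The interaction effects are ±(g - mean g)/2, so f² is the average over time of (g - mean g)²/4, in units of the single-measurement variance.
- Linear growth (0, d/2, d): f² = d²/24. Setting .0625 = d²/24 gives d = √1.5 = 1.22.
- Complete by week 2 (0, d, d), or arising only after week 2 (0, 0, d): f² = d²/18, so d = √1.125 = 1.06.

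Any monotone pattern from equal baselines lies between these. As partial eta-squared for the 6-df term at N = 40, the effect is 15/(15 + 72) = .172. For comparison, f = .40, the conventional large value, gives .16/1.16 = .138.

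**Step 3: the planned arm-by-time test.** Here df1 = 2 and df2 = 2(N - 4), which is 72 at N = 40 and 112 at N = 60. Power of .80 needs lambda of about 10.06 at N = 40 and 9.91 at N = 60. Then d = √(24 x lambda/(6N)) for linear growth and √(18 x lambda/(6N)) for the other patterns.

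| | N = 40 | N = 60 |
|---|---|---|
| Detectable d at .80, linear | 1.00 | 0.81 |
| Detectable d at .80, complete by week 2 | 0.87 | 0.70 |
| lambda at d = 0.5, linear (.25/24 x 6N) | 2.50 | 3.75 |
| Power at d = 0.5, linear | .26 | .38 |
| lambda at d = 0.5, complete by week 2 (.25/18 x 6N) | 3.33 | 5.00 |
| Power at d = 0.5, complete by week 2 | .34 | .49 |

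Simulating the 2 x 2 x 3 ANOVA (20,000 runs per setting) gave .267 and .339 at N = 40, and .387 and .493 at N = 60. A plain two-sample t-test at week 4 has power .34 and .48 for 0.5 SD.

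**Step 4: sensitivity.**
- With r = .70 instead of .50, the factor 3/(1 - r) rises from 6 to 10. Power for 0.5 SD becomes .42 to .53 at N = 40 and .59 to .72 at N = 60.
- If moderate is read on the SPSS scale (f = .25, partial eta-squared .0625/1.0625 = .059), lambda = .0625 x df2 = 4.5 and 7.0. Power is .44 at N = 40 and .64 at N = 60.

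No reading of moderate examined here other than f = .25 on the default scale reaches .80 at either N.

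**The case against.** The strongest reply is that nothing has been miscalculated: 40 is what the program returns for a conventional medium f on its default option. That stands. A reader might infer an arithmetic error, but the document does not show one.

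The document also never promises .80 power for a 0.5 SD difference between arms. Both f = .25 and 0.5 SD are supplied here. The match at 40 supports the first; nothing in the document supports the second beyond ordinary usage of the word moderate. That limits the point to a mismatch between label and power.

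A reader might also conclude that the trial is powered only for a difference of about 1 SD. That goes too far. The 1.06 to 1.22 SD belongs to the 6-df four-cell interaction behind the 40. The 2-df arm-by-time test is more sensitive: at f = .25 its power is .935 with 40 and .991 with 60, and at the sought 60 it has .80 power for 0.70 to 0.81 SD. Figures from the two tests must not be set side by side unlabelled. Likewise, a less than even chance of detecting a moderate effect at 60 holds for 0.5 SD at r = .50, not at r = .70 and not on the SPSS scale.

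Finally, one might infer that a null result will be reported as absence of benefit. The plan states no such conclusion: Data Analysis contains no equivalence claim, and Implications discusses what follows if a benefit is shown.

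**Conclusion.** Wrong as written, in the stated power. On the only reading found that yields 40 at the stated alpha, the effect called moderate is a week-4 arm difference of 1.06 to 1.22 SD. For the term that answers the treatment question, 40 participants detect 0.87 to 1.00 SD and 60 detect 0.70 to 0.81 SD with .80 power. A 0.5 SD difference would be detected with probability .26 to .34 at 40 and .38 to .49 at 60.

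The first conclusion rests on f = .25 and the default option, both inferred from the match. The power for 0.5 SD rests on treating that as moderate, and on r = .50, sphericity, equal cells, complete data and a common effect in both conditions. Dropout, or any adjustment across the four outcomes, would lower the figures; a higher correlation would raise them, though at r = .70 they still fall short of .80. The consequence is a claim of sensitivity that the design does not have, not an invalid analysis.

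**What to change.** Leave enrolment, procedures and analysis unchanged and restate the power paragraph in the Sample section. The sponsor should first confirm f and the option from its G*Power record. If they are as inferred, wording along these lines would do:

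*The total of 40 came from G*Power's within-between interaction (default effect-size option, f = .25, four groups, three measurements, correlation .50; 6 df). For the arm-by-time term (2 df, alpha .05, sphericity, equal cells, no dropout), power is .80 for a week-4 difference between arms of 0.87 to 1.00 SD with 40 participants and 0.70 to 0.81 SD with 60, depending on when the difference arises. For a 0.5 SD difference, power is .26 to .34 with 40 and .38 to .49 with 60.*

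This replaces the undefined effect label. If the 1.06 to 1.22 SD figure is also given, it should be labelled as belonging to the 6-df four-cell interaction. A sentence in Data Analysis saying that a non-significant arm-by-time result will not be read as excluding a moderate effect is optional.

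The cost is a few sentences and a less favourable stated power.
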